from 0.76 (95% CI: 0.74-0.79) to 0.89 (95% CI: 0.87-0.90). In separate work, [name] has identified quantitative imaging features in 146 ever smokers aged 50 to 80 years with incidentally-detected nodules from the UCLA EMR with high prediction performance (AUC-.86) in cross validation. Our preliminary data establishes the potential of both semantic and quantitative feature-based models for lung cancer.

	FSPG	FDG
Control	1.83±0.92	6.95±3.47
Case	7.52±6.68	14.35±6.03

Table 1. SUV_{max} with standard deviation for non-malignant lung

¹⁸F-FSPG PET tracer. Hijacking energy metabolism is a hallmark of cancer (10). ¹⁸F-FSPG is a glutamate analogue tracer that is transported into cells via the system xc^- transporter, which maintains the cellular redox environment (11). This transporter is also important in tumor growth, progression and treatment resistance (12, 13). ¹⁸F-FSPG visualizes distinct tumor biology compared to ¹⁸F-FDG, which measures cellular glucose uptake (14). Studies at Stanford have shown that lung cancer is well visualized by ¹⁸F-FSPG with low background uptake (2, 15). New data suggest that ¹⁸F-FSPG has lower uptake in many inflammatory conditions (16), which can severely limit ¹⁸F-FDG PET accuracy (**Table 1**). We therefore hypothesize here that ¹⁸F-FSPG is a superior tracer to assess the likelihood of cancer in pulmonary nodules.

Relevance of preliminary data: The preliminary data above establishes 1) our ability to measure a panel of mutations in ctDNA in early stage lung cancer, setting the stage for evaluating the panel as an early detection tool in the IPN setting; 2) nasal gene-expression as a potential diagnostic for lung cancer; 3) our ability to perform scRNA-seq of airway epithelial brushings in order to characterize the heterogeneity of the field; 4) semantic and quantitative imaging markers as diagnostic in the IPN setting; 5) the potential for novel molecular imaging markers to improve upon existing PET markers.

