10. MEASUREMENTS

10.1. Primary Outcome Measure (ClinicalTrials.gov)

The primary outcome is specificity of ¹⁸F-FSPG to discriminate between benign and malignant lung nodules, defined as the proportion of benign cases judged to be benign. With an expected 60 benign cases, an observed 90% specificity would have a 95% confidence interval of 79% to 96%. An observed specificity of 75% would have a confidence interval of 62-85%.

If a patient has multiple nodules, the per-patient assessment will be based on the dominant nodule only, defined as the largest nodule.

Outcome Title: ¹⁸F-FSPG specificity for malignant lung nodules.

Outcome Description: ¹⁸F-FSPG accumulation in lung nodules will be assessed. The observed FSPG specificity will be assessed against a fixed value of 75%.

Timeframe: Up to 5 years.

Safety Issue: No.

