PET Imaging: Patients will be imaged by ¹⁸F-FDG PET/CT and ¹⁸F-FSPG PET/CT. Uncorrected maximum lesion intensity (SUV_{max}) along with qualitative measures (absent, minimal, moderate, or high uptake) will be recorded. These data will be analyzed for lung cancer diagnosis using our prospective cohort study design. The person assessing SUV_{max} values and making the decisions about “positive” or “negative” will be blinded to the cancer status of the patient. We will maintain this by keeping the image reader blind to the patient information.

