11.2. Sample Size

Primary outcome: To compare 18F-FSPG PET/CT imaging with 18F-FDG PET/CT imaging for indeterminate lung nodules we will evaluate 120 patients. We estimate that approximately 60 of the patients will be diagnosed with lung cancer after complete diagnostic work-up and ~60 will not have lung cancer. Meta-analysis shows that 18F-FDG has a sensitivity and specificity of 89% and 75% respectively (16). We hypothesize that 18F-FSPG is more specific. With an expected 90% specificity for diagnosis with 18F-FSPG, a sample size of 60 will have 90% power at an alpha-level of 0.05 to demonstrate a significant increase in specificity from a fixed value of 75%.

Secondary outcome: In total the SU2C consortium cohort will be comprised of 930 study participants. Our Stanford group will contribute 120 (60 cases and 60 controls) to the larger sample set. Breakdown of the 930 patients are as follows. For the discovery step, sample size of 100 cases and 100 controls provides 80% power to detect RNA markers with effect sizes of at least 0.52 assuming that we will control the false discovery rate at 10% and 5% of markers are differentially expressed. For the refinement step, 75 cases and 75 controls provides 81% power to detect markers with a ROC AUC of at least 0.63 assuming an alpha level of 0.05. No correction for the multiple hypothesis testing is planned as we will re-evaluate top candidates. The sample size of 190 of each group for model building will support the following:

1. This sample size will be sufficient to include approximately 12 to 20 variables overall between clinical, imaging, ctDNA and gene expression markers based on conventional rules of thumb of 10 to 15 subjects per group per variable;
2. This will allow us to estimate the AUC for each model with a precision of approximately 4.5% (95% CI);
3. Provide 80% power for detecting delta AUCs between models of 0.06 assuming model correlation of 0.6.

For the model testing, 100 subjects in each group will provide AUC precision of ± 0.06 (and a precision of between 0.06 and 0.08 for the sensitivity and specificity), as well as a 80% power to detect differences in AUCs between models of 0.09. IRBs at the other sites have approved the collection of biospecimens and use of clinical / imaging data for this model development and validation work.

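### The primary test of FSPG specificity against 75% has no stated positivity rule and ignores sensitivity, so passing it would not show that FSPG discriminates better than FDG

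*Combined protocol and SAP*

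**What the plan says.** Objective 1.1 is comparative: it asks whether FSPG PET separates benign from malignant nodules better than FDG PET does.

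The primary outcome in section 10.1 is FSPG specificity, "defined as the proportion of benign cases judged to be benign". The comparison is with a constant: "The observed FSPG specificity will be assessed against a fixed value of 75" per cent. Section 11.2 sizes the study on that basis: "With an expected 90% specificity for diagnosis" with FSPG, "a sample size of 60 will have 90% power at an alpha-level of 0.05 to demonstrate a significant increase in specificity" from 75%. The 75% is the FDG specificity taken from a meta-analysis, which is also quoted as giving FDG a sensitivity of 89%.

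How a nodule comes to be judged benign is covered only in section 10.3 (PET Imaging). SUVmax "along with qualitative measures (absent, minimal, moderate, or high uptake) will be recorded". The person who makes the positive or negative decision "will be blinded to the cancer status of the patient".

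Sections 10 and 11 do not give an SUVmax cut-off, say which of the four visual grades count as positive, say which scale governs, or say when the rule is fixed. They set no endpoint or minimum for FSPG sensitivity. Section 11.4 makes a larger study depend on higher specificity than FDG, again without reference to sensitivity.

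**The concern.** Specificity belongs to a tracer together with a decision rule. A stricter rule raises it and misses more cancers; at the extreme, calling every nodule negative gives 100%. A success criterion that looks only at benign nodules cannot register that loss.

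Here the rule is unstated and two scales are recorded, so several operating points are open. The study could therefore exceed 75% because of where the line was drawn, and the result could be read as an answer to objective 1.1. Better discrimination involves both error rates, or a measure across all cut-offs, and it involves FDG in the same patients. The stated primary test uses none of these.

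**Working it through.** **1. The plan's own figures.** Inputs from sections 10.1 and 11.2: 60 benign cases, null 0.75, expected 0.90, alpha 0.05 (sidedness and test not stated).

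- Normal approximation with continuity correction, one-sided 0.05. Critical count = 60×0.75 + 0.5 + 1.645×√(60×0.75×0.25) = 45 + 0.5 + 5.52 = 51.02. Power = Φ[(54 − 51.02)/√(60×0.9×0.1)] = Φ(2.98/2.324) = 0.900. The stated 90% reproduces.
- One-sided exact test: success at 51 or more of 60, with P = 0.045 if specificity is 75% and 0.927 if it is 90%.
- The interval also reproduces. The plan says: "With an expected 60 benign cases, an observed 90% specificity would have a 95% confidence interval of 79% to 96" per cent. Clopper-Pearson for 54/60 gives 79.5% to 96.2%.

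The sample-size arithmetic is not in question. I use 51 of 60 as the success count below.

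**2. How far specificity moves with the cut-off.** Inputs from Table 1, section 2.5 (mean ± SD of SUVmax, FSPG then FDG): "Control 1.83±0.92 6.95±3.47"; cases 7.52±6.68 (FSPG) and 14.35±6.03 (FDG). The shape of the distributions is not given, so it is an assumption. Normal, log-normal and gamma were each matched to the mean and SD.

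For the normal, cut-off = mean + z × SD: 1.83 + 0.6745×0.92 = 2.45 for 75%, and 1.83 + 1.2816×0.92 = 3.01 for 90%. For the log-normal, σ² = ln[1 + (0.92/1.83)²] = 0.225 and μ = ln 1.83 − σ²/2 = 0.492, so the cut-offs are exp(0.492 + 0.6745×0.475) = 2.25 and exp(0.492 + 1.2816×0.475) = 3.00. For the gamma, shape = (1.83/0.92)² and scale = 0.92²/1.83.

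| Shape | FSPG cut-off, 75% specificity | FSPG cut-off, 90% specificity | Gap |
|---|---|---|---|
| Normal | 2.45 | 3.01 | 0.56 |
| Log-normal | 2.25 | 3.00 | 0.75 |
| Gamma | 2.34 | 3.06 | 0.72 |

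By construction, the chance of 51 or more benign calls goes from 4.5% to 92.7% across each gap. If 52 of 60 is required (two-sided exact), it goes from 2.1% to 85.8%. The gap is 10% to 13% of the difference between case and control means (7.52 − 1.83 = 5.69).

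**3. What the success rule does not see.** For FSPG sensitivity I use only the log-normal and gamma shapes. The normal puts Φ(−7.52/6.68) = 13% of cancers below an SUV of zero, so it is unusable for cases.

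| FSPG cut-off | Log-normal: specificity / sensitivity | Gamma: specificity / sensitivity |
|---|---|---|
| At 75% specificity | 75% / 88% | 75% / 78% |
| At 90% specificity | 90% / 79% | 90% / 71% |
| 4.0 | 97% / 67% | 97% / 63% |

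At 4.0 the primary test is passed almost with certainty, while about a third of cancers are called negative.

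**4. The same arithmetic applied to FDG.** Normal: cut-off = 6.95 + 1.2816×3.47 = 11.40; sensitivity = 1 − Φ[(11.40 − 14.35)/6.03] = 69%. Log-normal: 11.38 and 65%. Gamma: 11.60 and 64%. (For FDG cases the normal puts only Φ(−14.35/6.03), under 1%, below zero.) Read at such a cut-off, FDG would itself have 90% specificity and a 92.7% chance of passing the test against 75%. A test that the comparator can pass does not identify the better tracer.

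**The case against.** **Blinding.** The reader does not know the cancer status, so calls on individual scans cannot follow the diagnosis. This stands. A reader might infer from the missing rule that calls could be steered patient by patient; section 10.3 rules that out. Blinding does not set the operating point, though, and nothing says that the rule is fixed before diagnoses are linked.

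**The size of the gap is generic.** In any normal distribution the 75th and 90th percentiles lie 0.61 SD apart, so some such gap exists for every continuous marker. Whether it is small depends on the scale: 0.56 is 23% of the 2.45 cut-off. Agreed. The figures show that specificity alone is not interpretable without a rule; they are not evidence of a weakness peculiar to FSPG.

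**Table 1 is thin.** It gives no numbers of patients, its caption breaks off in the available text, and its controls may not resemble 7 to 30 mm indeterminate nodules. If the call is purely visual, the SUV arithmetic is only an analogue. All true, but the gap in the text does not depend on Table 1: the plan does not say whether minimal uptake is positive.

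**FSPG would miss more cancers than FDG.** A reader might infer this by setting the modelled FSPG sensitivities beside the quoted 89%. The documents do not support it. The 89% comes from a meta-analysis and the FSPG figures from Table 1. Within Table 1, at 90% specificity, FSPG is ahead (71% to 79% against 64% to 69%). At 75% specificity the order depends on the assumed shape (log-normal 88% against 86% for FDG; gamma 78% against 82%).

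**The study is exploratory.** Section 2.6 calls it so, section 2.4 describes the PET part as a pilot, and success leads only to planning a larger study. Making specificity the hypothesis is a legitimate choice, and the wish for a sensitive marker with high negative predictive value is general motivation. I therefore do not claim that the endpoint contradicts it. The study does, however, carry a powered primary hypothesis and a go-forward rule, and its stated objective is comparative.

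**Conclusion.** The point holds. The primary success rule takes no account of sensitivity, and the positive or negative call has no stated link to SUVmax or to the visual grade. Passing it would show that FSPG specificity exceeds 75% at some unstated operating point, not that FSPG discriminates better than FDG.

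The size is illustrative. Under three assumed shapes fitted to Table 1, a shift of under one SUV unit carries the primary test from near-certain failure to its planned power, and FDG could pass the same test at a suitable cut-off. The textual finding rests on sections 10.1, 10.3, 11.1, 11.2 and 11.4; only the magnitude rests on Table 1.

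Two stronger conclusions do not follow: that FSPG is expected to be less sensitive than FDG, and that the sample size is wrong. The first mixes sources, and the stated power reproduces.

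**What to change.** 1. In sections 10.1 and 10.3, name one positivity rule for FSPG (which scale, and which cut-off or grades, as the investigators choose) and state that it is locked before any reference diagnosis is linked to the images.
2. Report FSPG sensitivity with its 95% CI at that same rule, beside specificity. With about 60 cancers the precision is similar: 53/60 (88%) would give 77% to 95%.
3. Add a paired comparison of SUVmax AUC, FSPG against FDG, by DeLong's method, in all patients with both scans and a reference diagnosis. Name it as the analysis that answers objective 1.1. Base any statement that FSPG discriminates better on this comparison, not on specificity against 75% alone.

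I do not propose a joint success criterion: the documents give no minimum sensitivity on which to build one.

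Cost: wording and one extra analysis. Both scans are already planned for all 120 patients (section 2.6), and DeLong's test is already named for the secondary outcome (section 10.2). The specificity test keeps its 60 benign cases and its power. The real price is that a superiority statement becomes harder to reach. Section 11.2 gives 80% power for an AUC difference of 0.09 with 100 per group. Scaled by √(100/60) = 1.29, that is about 0.12 with 60 per group, on the assumption that AUC levels and correlation are alike. The paired difference should therefore be reported with its confidence interval, whatever its p-value.

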1. OBJECTIVES

1.1. Primary Objective

Comparison of ¹⁸F-FSPG accumulation with ¹⁸F-FDG accumulation to assess whether (4S)-4-(3-¹⁸F-Fluoropropyl)-L-Glutamate (¹⁸F-FSPG) PET is better at discriminating between benign and malignant nodules.

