2.6. Study Design

120 patients with indeterminate lung nodules will be enrolled in the study at Stanford. Blood and nasal brushings will be collected once. The samples from these 120 patients will be part of a bigger cohort of over 900 patients for collaborative data analysis.

All samples will be de-identified before shipment or other data sharing with collaborators takes place. An additional 70 patients who may or may not have smoking history will be imaged at Stanford and analyzed with the other 50 patients enrolled at Stanford.

All 120 patients will be imaged once by ¹⁸F-FSPG PET/CT as part of this open-label, nonrandomized, single-dose explorative study and once by ¹⁸F-FDG PET/CT. PET/CT imaging will be scheduled > 24 hours apart to allow for imaging agent washout, and not more than two weeks apart to allow for optimal image comparison.

Clinical diagnosis (cancer / benign disease) is based on 1) histopathology of biopsy/surgical specimen or 2) surveillance by CT scans for a period of 2 years to confirm that there is no

¹⁸F-FSPG PET/CT and Integrated Biomarkers for Early Lung Cancer Detection in Patients with Indeterminate Pulmonary Nodules

growth of the nodule. All patients without histopathological diagnosis will undergo CT surveillance for a 2-year period by clinical standards.

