4. IMAGING AGENT AND PROCEDURE INFORMATION

4.1. Imaging Agent and Imaging Procedure

Patients enrolled in this study will undergo a one-time ¹⁸F-FSPG PET/CT procedure which includes a single IV injection of ¹⁸F-FSPG. Patients will also undergo one ¹⁸F-FDG PET/CT as part of their standard of care. The two PET/CT procedure will be scheduled > 24 hours apart to allow for imaging agent washout, and not more than two weeks apart.

The nuclear physician or designee is responsible for ensuring that deliveries of the imaging agent and other materials from the manufacturing site are correctly received, recorded, handled, and stored safely and properly in accordance with all applicable regulatory guidelines, and used in accordance with this protocol.

Unless otherwise agreed, imaging agent vials must be destroyed on-site after use. The transport containers have to be returned to the manufacturing site. A list of imaging agent or other materials that were returned, or destroyed, must be prepared and signed by the principal investigator or designee. If there are any discrepancies, an explanation for these should also be provided

Physical, Chemical and Pharmaceutical Properties of the Imaging Agent

IUPAC name: (S)- 4-(3-[¹⁸F]Fluoropropyl)-L-glutamic acid

Chemical name: (2S, 4S)-2-Amino-4-(3-[¹⁸F]-fluoro propyl) pentane dioic acid

Empirical formula: C₈H₁₄FNO₄

Molecular weight: 206.2 g/mol

The active pharmaceutical ingredient for PET/CT imaging is the compound ¹⁸F-FSPG that is labeled with the radioactive fluoride isotope ¹⁸F. ¹⁸F has a half-life of 110 minutes. The radioactive substance and the final imaging product are produced on-site at the study site

¹⁸F-FSPG PET/CT and Integrated Biomarkers for Early Lung Cancer Detection in Patients with Indeterminate Pulmonary Nodules

according to the radiolabeling and purification procedure described in the site Standard Operating Procedures (SOPs) and the Investigational New Drug application (IND). The Department of Chemistry, Manufacturing, Controls (CMC) personnel of Stanford will train qualified radiochemists/pharmacists with respect to the imaging agent production and handling. The precursor PI-020 and a non-radioactive standard used as a reference for Quality Assurance, and corresponding Certificates of Analysis will be provided by Piramal Imaging, SA.

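### Section 10.3 does not state that each PET tracer is read blind to the other, so FSPG calls could be made with the FDG result in view

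*Combined protocol and SAP*

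**What the plan says.** Section 10.3 (PET Imaging) holds the plan's only text on reader blinding. The person who measures SUVmax and makes the call "will be blinded to the cancer status of the patient". The means is then given: "keeping the image reader blind to the patient information". Patient information is not defined, and the other tracer's scan is not mentioned.

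The same paragraph sets out the data: "Patients will be imaged by ¹⁸F-FDG PET/CT and ¹⁸F-FSPG PET/CT". SUVmax is recorded "along with qualitative measures (absent, minimal, moderate, or high uptake) will be recorded". No cut-off or rule turns either measure into a positive or negative call.

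Other sections give the setting:

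- Section 4.1: "Patients will also undergo one ¹⁸F-FDG PET/CT as part of their standard of care".
- Section 2.6: the scans are more than 24 hours apart and "not more than two weeks apart to allow for optimal image comparison".
- Section 6: the order of the two scans is not fixed.
- Section 10.1: the primary outcome is FSPG specificity in benign cases, a judged call, tested against a fixed 75%.
- Section 1.1: the primary objective compares FSPG with FDG uptake "to assess whether (4S)-4-(3-¹⁸F-Fluoropropyl)-L-Glutamate (¹⁸F-FSPG) PET is better at discriminating between benign and malignant nodules".
- Section 11.4: a larger study follows if FSPG is more specific than FDG.

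**The concern.** A site could follow section 10.3 to the letter and still read the two scans side by side, or read FSPG after FDG. With no positivity rule, the FSPG call is open to influence from whatever else the reader has seen.

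Two things are at stake. The first is the primary outcome itself. If a reader carries an FDG-positive impression over to a benign nodule, FSPG specificity is pulled down. If a negative FDG scan reassures the reader about a doubtful FSPG finding, it is pushed up. The second is the comparison of tracers in sections 1.1 and 11.4. Reads made with knowledge of each other are dependent, so agreement or disagreement between tracers partly reflects the reading process. Once joint reading has taken place, independence cannot reliably be restored in the analysis.

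**Working it through.** **Inputs from the plan (sections 10.1, 11.1, 11.2).** 60 expected benign cases; fixed value 75%; expected FSPG specificity 90%; FDG specificity 75%; alpha 0.05; stated power 90%. Sidedness is not stated.

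**Reproducing the stated power.** One-sided normal approximation with continuity correction:

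- standard error at 75%: √(0.75 × 0.25 / 60) = 0.0559
- standard error at 90%: √(0.90 × 0.10 / 60) = 0.0387
- z = (0.15 − 1/120 − 1.645 × 0.0559) / 0.0387 = 1.284, so power = 90.0%

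The stated 90% reproduces. This point disputes no figure in the plan.

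**Exact success boundaries.** These are the smallest r with P(X ≥ r | 60, 0.75) within the limit. One-sided 0.05 gives r = 51 (actual level 4.5%). Two-sided 0.05, upper tail 0.025, gives r = 52 (2.1%). The plan states neither boundary.

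**Illustration 1: a fixed number of changed calls.** Assume that 2 or 3 of 60 benign calls change, all in one direction. Apparent specificity then shifts by 2/60 or 3/60, and P(X ≥ r | 60, p) gives:

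| True specificity | Calls changed | Apparent p | One-sided (≥ 51/60) | Two-sided (≥ 52/60) |
|---|---|---|---|---|
| 90% (power) | 0 | 0.900 | 93% | 86% |
| 90% | 2 to positive | 0.867 | 73% | 59% |
| 90% | 3 to positive | 0.850 | 59% | 44% |
| 75% (false success) | 0 | 0.750 | 4.5% | 2.1% |
| 75% | 2 to negative | 0.783 | 13% | 7.4% |
| 75% | 3 to negative | 0.800 | 21% | 12.7% |

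**Illustration 2: a share of calls influenced.** This is a cross-check with a different mechanism.

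- *Downward.* A share f of benign FSPG calls simply follows an FDG read with 75% specificity: p = (1 − f) × 0.90 + f × 0.75. For f = 10%, 20%, 30%, p is 88.5%, 87.0%, 85.5%. Power is 85.3%, 75.2%, 63.0% (one-sided) or 75.1%, 62.3%, 48.8% (two-sided).
- *Upward.* True FSPG specificity is 75%, the tracers are independent in benign nodules, and a share g of FSPG false positives with a negative FDG read is re-called negative: p = 0.75 + g × 0.25 × 0.75. For g = 10%, 20%, 30%, false success is 8.6%, 15.2%, 25.0% (one-sided) or 4.4%, 8.5%, 15.3% (two-sided).

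**Linking the two.** In the downward case the expected net change is 60 × f × 0.15 = 9f calls, so 2 or 3 calls correspond to f of about 22% or 33%. In the upward case it is 60 × g × 0.1875 = 11.25g calls, so 2 or 3 calls correspond to g of about 18% or 27%. The documents give no rate of influence. These figures show how sensitive the test is, not how likely the change is.

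**The case against.** **The plan is silent; it does not permit joint reading.** A reader might infer that the reader is masked to cancer status and nothing else, or that the same person will see both scans together. The text supports neither. Patient information could be taken to include a previous FDG result, and the person in section 10.3 is a role, not proof of one reader for both tracers. This stands, and the point is limited to what is not stated. But the phrase serves the masking of cancer status, and it does not clearly cover the other tracer's images: de-identified scans can still be viewed together.

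**The FDG report.** A reader might assume that a clinical FDG report will be to hand. The documents say only that FDG is standard of care, so the point does not rest on a report.

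**The success boundary.** It is tempting to treat 52 of 60 as the plan's threshold. It assumes a two-sided test; one-sided, the threshold is 51. Both are shown above.

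**False success does not follow from sight of FDG alone.** If both tracers have 75% specificity and the reader simply copies FDG, apparent FSPG specificity stays at 75%. Inflation needs changes in one direction. A reader who expects FSPG to be more specific could also produce it without seeing FDG, and masking the FDG scan would not remove that. This stands, so those figures are conditional.

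**The primary test is not paired, and SUVmax is a measurement.** Both are true: the test is against a fixed 75% in an explorative study, with no paired test specified. The FSPG calls are nevertheless the data for that test. SUVmax is less open to influence than a four-level grade, but without a stated cut-off it protects the call little.

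**Conclusion.** The point holds as a gap in the blinding rule. Section 10.3 masks cancer status but does not state that each tracer is read blind to the other, while the design gives every patient both scans close together and rests the primary outcome on a judged call. Bias in FSPG specificity could go either way, and the comparison in sections 1.1 and 11.4 could rest on dependent reads.

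The size is illustrative. Two or three changed calls in 60, all in one direction, are enough to cut power by roughly 20 to 41 percentage points or to raise false success to about three to six times its nominal-rule value, across the one-sided and two-sided tests. This rests on the assumed number and direction of changed calls. It does not show that such influence will occur. The sample size need not change. The amendment should be made before images are read, because the remedy is cheap and joint reads cannot be undone.

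**What to change.** Amend section 10.3 to state that:

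1. each patient's FSPG and FDG scans are read as de-identified studies in separate sessions;
2. each read is made without the other tracer's images or report and without the clinical work-up, as well as blind to cancer status;
3. FSPG calls are recorded and locked before any joint review of the two scans.

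The same reader can do both reads. Random reading order and a set washout between sessions are useful but optional. The cost is reading logistics and one paragraph of text, with no extra scan, patient or reader.
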